9. STATISTICAL SOFTWARE

SAS Version 9.4 or later will be used for all statistical analyses.

The PK parameters will be estimated by noncompartmental analysis (NCA) using the software Phoenix® WinNonlin® version 8.1 (Certara, USA).

11. APPENDIX 1 NCI-CTCAE V4.03 TOXICITY GRADING

11.1 Panel: Chemistry

Lab Test	Unit	Grade 1	Grade 2	Grade 3	Grade 4
Albumin, serum- low (hypoalbuminemia)	g/L	[30, LLN)	[20, 30)	<20	life-threatening consequences; urgent intervention indicated
Alkaline phosphatase (ALK) increased	U/L	(ULN, 2.5*ULN]	(2.5*ULN, 5*ULN]	(5*ULN, 20*ULN]	>20*ULN
Alanine aminotransferase (ALT) increased	U/L	(ULN, 3.0*ULN]	(3.0*ULN, 5.0*ULN]	(5*ULN, 20*ULN];	>20*ULN
Aspartate aminotransferase (AST) increased	U/L	(ULN, 3.0*ULN]	(3.0*ULN, 5.0*ULN]	(5*ULN, 20*ULN];	>20*ULN
Bilirubin increased	µmol/L	(ULN, 1.5*ULN]	(1.5*ULN, 3*ULN]	(3*ULN, 10*ULN]	>10*ULN
Calcium high (hypercalcemia)	mmol/L	(ULN, 2.9]	(2.9, 3.1]	(3.1, 3.4]; hospitalization indicated	>3.4; life-threatening consequences
Calcium low (hypocalcemia)	mmol/L	[2.0, LLN)	[1.75, 2.0)	[1.5, 1.75); hospitalization indicated	[0, 1.5); life threatening consequences
Creatine phosphokinase (CPK) increased	U/L	(ULN, 2.5*ULN]	(2.5*ULN, 5*ULN]	(5*ULN, 10*ULN]	>10*ULN
Creatinine increased	µmol/L	(1 – 1.5*baseline]; (ULN, 1.5*ULN]	(1.5 – 3.0* baseline]; (1.5*ULN, 3*ULN]	>3.0*baseline; (3*ULN, 6*ULN]	>6*ULN
Gamma-glutamyl-transferase	U/L	(ULN, 2.5*ULN]	(2.5*ULN, 5*ULN]	(5*ULN, 20*ULN]	>20*ULN
Glucose high (hyperglycemia)	mmol/L	(ULN, 8.9]	(8.9, 13.9]	(13.9, 27.8]; hospitalization indicated	>27.8; life threatening consequences
Glucose low (hypoglycemia)	mmol/L	[3.0, LLN)	[2.2, 3.0)	[1.7, 2.2)	[0, 1.7); life threatening consequences; seizures

Lab Test	Unit	Grade 1	Grade 2	Grade 3	Grade 4
Magnesium low (hypomagnesemia)	mmol/L	[0.5, LLN)	[0.4, 0.5)	[0.3, 0.4)	<0.3; life-threatening consequences
Magnesium high (hypermagnesemia)	mmol/L	(ULN, 1.23]	undefined	(1.23, 3.3]	>3.3; life-threatening consequences
Phosphates (hypophosphatemia)	mmol/L	[0.8, LLN)	[0.6, 0.8)	[0.3, 0.6)	[0, 0.3); life threatening consequences; seizures
Potassium high (hyperkalemia)	mmol/L	(ULN, 5.5]	(5.5, 6]	(6, 7]; hospitalization indicated	>7; life-threatening consequences
Potassium low (hypokalemia)	mmol/L	[3, LLN)	[3, LLN); symptomatic; intervention indicated	[2.5, 3); hospitalization indicated	[0, 2.5); life-threatening consequences
Sodium high (hypernatremia)	mmol/L	(ULN, 150]	(150, 155]	(155, 160]; hospitalization indicated	>160; life-threatening consequences
Sodium low (hyponatremia)	mmol/L	[130, LLN)	undefined	[120, 130)	[0, 120); life-threatening consequences

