3 OBJECTIVES AND ENDPOINTS

OBJECTIVES	ENDPOINTS	JUSTIFICATION
Primary		
Monotherapy Dose Escalation: Determine a maximum tolerated dose (MTD) or recommended Phase 2 dose (RP2D) for ZN-c5 as a monotherapy Monotherapy Expansion: Investigate the safety and tolerability of ZN-c5 as a monotherapy in subjects with Estrogen Receptor (ER) positive, Human Epidermal Growth Factor Receptor-2 (HER2) negative advanced breast cancer	Observed Dose Limiting Toxicities Safety and tolerability as measured by incidence of treatment-emergent AEs and lab abnormalities	This is accepted methodology to evaluate safety and determine the doses for further evaluation. The incidence of treatment emergent AEs and lab abnormalities reflects the safety profile of ZN-c5.
Combination Dose Escalation: Determine an MTD or RP2D for ZN-c5 when administered in combination with palbociclib	Observed Dose Limiting Toxicities	
Monotherapy Phase 2: Determine preliminary anti-tumor efficacy (Clinical Benefit Rate [CBR]) for ZN-c5 as a monotherapy Combination Phase 2: Determine preliminary anti-tumor efficacy (CBR) for ZN-c5 when administered in combination with palbociclib	CBR (CR [+ PR] + SD ≥ 24 weeks). PR will only be included for patients with measurable disease.	ZN-c5 is expected to have activity in the selected patient population, and standard measures of disease response/progression were chosen to evaluate potential efficacy.
Secondary		
 Monotherapy Dose Escalation and Phase 2: Investigate the safety and tolerability of ZN-c5 as a monotherapy in subjects with ER positive, HER2-negative advanced breast cancer Combination Dose Escalation and Phase 2: Investigate the safety and tolerability of ZN-c5 in combination with palbociclib in subjects with ER positive, HER2 negative advanced breast cancer 	All Cohorts: Safety and tolerability as measured by incidence of treatment-emergent AEs and lab abnormalities	The incidence of treatment-emergent AEs and lab abnormalities reflects the safety profile of ZN-c5 across all subjects in the study.

OBJECTIVES	ENDPOINTS	JUSTIFICATION

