- d) Subjects who will undergo a FES-PET must have discontinued all prior ER blocking therapy (e.g., tamoxifen or fulvestrant) for ≥ 60 days before the day of the examination at baseline.
- In counting lines of treatment for advanced/metastatic disease, any change in regimen due to PD or toxicity will be counted as a separate line of treatment.
- 9) Documented prior response to endocrine therapy for advanced or metastatic disease (SD, PR, or CR) lasting > 6 months or disease recurrence after at least 24 months of adjuvant endocrine treatment. (not required for treatment naïve patients)
- 10) Prior Chemotherapy:
 - a) [Monotherapy Dose Escalation Cohort]: Up to 2 prior lines of chemotherapy for the treatment of advanced breast cancer
 - b) [Monotherapy Phase 2]: No prior chemotherapeutic regimens for the treatment of advanced breast cancer
 - c) [Monotherapy Expansion, Combination Dose Escalation and Combination Phase 2 Cohorts]: Up to 1 prior line of chemotherapy for the treatment of advanced breast cancer

In counting lines of treatment for advanced/metastatic disease, any change in regimen due to PD or toxicity will be counted as a separate line of treatment.

- 11) Prior treatment with a CDK4/6 inhibitor is allowed
- 12) Evaluable or measurable disease per RECIST v1.1.
- 13) Eastern Cooperative Oncology Group (ECOG) Performance Status of ≤ 2
- 14) All acute toxic effects of any prior anti-tumor therapy resolved to Grade ≤ 1 or baseline (with the exception of alopecia [any grade permitted])
- 15) Adequate organ function defined as follows:
 - a) Hematologic: Platelets $\geq 100 \times 10^9$ /L; Hemoglobin ≥ 9.0 g/dL; Absolute Neutrophil Count (ANC) $\geq 1.5 \times 10^9$ /L (without platelet transfusion or any growth factors within previous 7 days of the hematologic laboratory values obtained at Screening visit).
 - b) Hepatic: Aspartate transaminase (AST) and Alanine transaminase (ALT) ≤ 2.5 × upper limit of normal (ULN) or ≤ 5 × ULN in case of liver metastases; Total or conjugated bilirubin ≤ 1.5 × ULN.
 - c) Renal: Creatinine clearance (CrCl) ≥ 30 mL/min as calculated by the Cockcroft Gault method or serum creatinine ≤ 1.5 × ULN
- 16) [Premenopausal and perimenopausal female subjects]: Negative serum pregnancy test
- 17) Male and female subjects of childbearing potential or partners of subjects who engage in intercourse must agree to use protocol specified method(s) of contraception.

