6. STATISTICAL METHODS

6.1 General Data Handling Rules and Definitions

All data collected on case report forms will be provided in listings, except data collected only for confirmation of study entry criteria and for study administrative purposes. If any enrolled subject is found not having valid documented informed consent, that subject's data will be excluded from the report, except as necessary to document the error.

All analyses will be conducted using SAS version 9.4 or later.

Summary tables for continuous variables will include the following statistics: n (sample size), mean, standard deviation, 95% CIs on the mean (where applicable), median, minimum and maximum. Summary tables for categorical variables will include: n, proportion and 95% CIs on the proportion (where applicable). Unless otherwise indicated, 95% CIs for binary variables will be calculated using the binomial distribution (exact method) and will be 2-sided.

Endpoints will be summarized by relevant study part (escalation, expansion, Phase 2), actual dose level received (on the first day of treatment), therapy (mono or combination), analysis set and time point. As appropriate, changes from Baseline to each subsequent timepoint will be described and summarized. Similarly, as appropriate, the best/worst change from Baseline during the study will also be described and summarized.

The Baseline value will be the last (most recent) pre-treatment value. If there is a significant degree of non-normality, analyses may be performed on log-transformed data or nonparametric tests may be applied, as appropriate.

Missing data will be maintained as missing unless specified otherwise. For variables where missing data is imputed, the analysis dataset will contain one variable with the imputed value and the original variable with missing maintained as missing.

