Hematology, serum chemistry and coagulation tests will be programmatically graded according to NCI-CTCAE v4.03 toxicity grading as detailed in [Appendix 1 NCI-CTCAE V4.03 Toxicity Grading](#) when applicable. For parameters for which a CTCAE scale does not exist, reference ranges from the local laboratory will be used to determine programmatically if a laboratory parameter is below, within or above the normal range for the subject’s age, sex, etc.

Treatment-emergent laboratory abnormalities will be identified and will be the focus of laboratory data summarization. A treatment-emergent laboratory abnormality is defined as an abnormality that, compared to baseline, worsens by ≥ 1 grade in the period from the first dose of study drug to 30 days after the last dose of study drug. If baseline data are missing, then any graded abnormality (i.e., an abnormality that is Grade ≥ 1 in severity) will be considered treatment-emergent.

For laboratory results entered with inequality symbols ($<$, \leq , $>$, \geq), numeric values will be imputed by ignoring the inequality symbol(s) (e.g. “ <1.71 ” will be imputed as 1.71 for numeric analyses). Imputed values will not be listed in data listings.

For each laboratory test, Baseline and worst (maximum) CTCAE grade post-Baseline will be identified for each subject. For parameters for which a CTCAE scale does not exist, the Baseline and worst post-Baseline value will be identified as being below, within or above the normal range as detailed above. Change from Baseline will be calculated for all post-Baseline results.

Subjects will be characterized only once for a given assay, based on the worst severity grade observed during a period of interest (e.g., during the study or from Baseline to a particular visit).

Hematology, coagulation and serum chemistry data, and changes from Baseline will be summarized by dose level, by visit for visits from Baseline to C2D1 as well as EOT. Urinalysis and pregnancy test results will be listed only. Plasma 4 β -hydroxycholesterol and cholesterol will be listed only.

Shift tables for hematology, coagulation and serum chemistry will also be presented by showing change in CTCAE severity grade from Baseline to worst grade post-Baseline. A shift table for hematology showing change in CTCAE severity grade from Baseline to worst Cycle 1 value will also be presented.

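### The Grade 1 creatinine row in SAP Appendix 1 counts any rise above a single baseline value, so chance alone makes a large share of subjects with normal creatinine treatment-emergent Grade 1

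*SAP*

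**What the plan says.** The Grade 1 cell for increased creatinine in SAP 11.1 has two limbs: "1 – 1.5*baseline]; (ULN, 1.5*ULN". One is relative to the subject's own baseline, the other to ULN. The Grade 2 and Grade 3 cells also carry baseline limbs, but these start at 1.5 and 3 times baseline.

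Four other rules determine how the cell acts:

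- SAP 6.6.4, grading: "Hematology, serum chemistry and coagulation tests will be programmatically graded according to NCI-CTCAE v4.03 toxicity grading as detailed in" Appendix 1.
- SAP 6.6.4, worst value: "Baseline and worst (maximum) CTCAE grade post-Baseline will be identified for each subject". SAP 6.6.1 lets unscheduled values enter worst-case analyses.
- SAP 6.6.4, emergence: "A treatment-emergent laboratory abnormality is defined as an abnormality that, compared to baseline, worsens by ≥ 1 grade".
- SAP 6.1, baseline: "The Baseline value will be the last (most recent) pre-treatment value". This is one measurement, not an average.

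Protocol section 3 gives the primary endpoint of the Monotherapy Expansion as "Safety and tolerability as measured by incidence of treatment-emergent AEs and lab abnormalities". The same measure is a secondary endpoint for all cohorts.

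**The concern.** A subject with normal creatinine is Grade 0 at baseline: the ratio to baseline is 1 and the value is not above ULN. The first later value that is higher by any reportable amount is at least Grade 1, even in the middle of the normal range. Because the worst grade is taken over all draws, a single such value is enough. No minimum rise or repeat measurement is required.

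The rule also acts unevenly. Protocol 5.1 admits subjects on "Creatinine clearance (CrCl) ≥ 30 mL/min as calculated by the Cockcroft Gault method or serum creatinine ≤ 1.5 × ULN", so some may enrol with creatinine above ULN. They start at Grade 1, and the same small rise does not flag them. The chance flags therefore fall on subjects with normal baseline creatinine.

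At stake is the meaning of one line in a laboratory summary that belongs to a primary endpoint. A Grade 1 creatinine incidence built this way mostly measures how often a subject was sampled and how finely the laboratory rounds.

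**Working it through.** The documents give no expected rate of creatinine abnormality, so there is no plan figure to reproduce.

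**Step 1: the rule on one subject.** Assume ULN 90 µmol/L, baseline 68 and a later value of 69. The ratio is 69/68 = 1.015, inside the Grade 1 baseline limb. Grade 0 becomes Grade 1, which is treatment-emergent, although 69 is well below ULN.

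**Step 2: number of post-baseline draws, n** (Schedule of Activities, scheduled monotherapy visits).

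- n = 3: C1D8, C1D15, C2D1.
- n = 6: add C3D1, End of Treatment and Safety Follow-up.
- n = 9: add C4D1, C5D1 and C6D1.

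Unscheduled draws, and C2D15 in the combination parts, raise n.

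**Step 3: exact rate with no drug effect and no ties.** Baseline and the n later values are exchangeable, so baseline is the highest of the n+1 values with probability 1/(n+1). Hence

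P(at least one later value above baseline) = n/(n+1).

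This gives 3/4 = 75%, 6/7 = 86% and 9/10 = 90%, whatever the size of the noise. Restricting to baselines at or below ULN raises these slightly, because it favours low baselines.

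**Step 4: ties from rounding.** This needs assumptions that the documents do not supply. With mean 68, SD 11, ULN 90 µmol/L and within-subject CV 4–8%, for baseline at or below ULN and n = 3 to 9:

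- whole-µmol/L reporting: about 70–90% flagged;
- 0.1 mg/dL reporting: about 31–51% (n=3), 41–64% (n=6) and 46–70% (n=9);
- ULN limb alone: about 1–10%.

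About 89–97% of flagged subjects never exceed ULN.

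A second set of assumptions (mean 70, SD 10, same ULN and CV range; 200,000 simulated subjects per setting; baseline at or below ULN) agrees:

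| Reporting unit | n | Rule as written | ULN limb alone |
|---|---|---|---|
| 1 µmol/L | 3 | 70.7–74.3% | 2.9–7.0% |
| 1 µmol/L | 6 | 82.7–85.5% | 4.2–10.7% |
| 0.1 mg/dL | 3 | 32.6–52.7% | 1.8–5.0% |
| 0.1 mg/dL | 6 | 42.8–66.3% | 2.8–8.0% |

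**Step 5: how far up the scale the noise reaches.** In the same runs, for n up to 10, chance took a value above 1.5 times baseline in at most about 0.2% of subjects. The inflation stops at Grade 1.

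**Step 6: the semicolon.** If the two limbs had to hold together, a value at 2 × baseline and 1.2 × ULN would have no grade: Grade 1 fails because 2 exceeds 1.5, and Grade 2 fails because 1.2 × ULN is below 1.5 × ULN. Only *or* grades every raised value.

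**The case against.** **It is the scale that the protocol asks for.** Protocol 9.4.4.3 requires programmatic CTCAE grading, and Appendix 1 presents the row as v4.03. This stands. A reader might infer a transcription error, but the source scale is not among the documents and nothing in them shows one. The problem is how the row combines with a single baseline, the worst value and a one-grade rule. In the same appendix, the row for increased hemoglobin uses baseline only when baseline is above ULN; the creatinine row has no such guard.

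**The footnote may switch the limb off.** The note under 11.4 says that conditions are not checked by program. In the text as extracted it is not tied to any row, and a marker may have been lost. The clinical-text cells are its likelier target, since the baseline limb is a numeric bound. The text cannot settle this, so the SAP should.

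**The rate is not one number.** This stands. Each site's own laboratory runs chemistry, at about 60 centers, and the documents do not fix reporting precision. A reader might infer that most subjects will be flagged everywhere. That follows for fine reporting, but not for reporting to 0.1 mg/dL at few draws.

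**A renal signal would still be visible.** This also stands. A reader might infer that the rule hides real toxicity. However, shift tables keep Grade 2 and Grade 3 apart from Grade 1, changes from baseline are summarised by visit to C2D1 and at End of Treatment, and calculated creatinine clearance is a separate analyte. Nor is growth with more draws peculiar to this rule: the ULN limb's rate also rises with n.

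**Conclusion.** The point holds, with a limited scope. Followed as written, the SAP counts a subject with baseline creatinine at or below ULN as treatment-emergent Grade 1 by chance alone with probability about n/(n+1). After rounding, that is about 70–90% at whole-µmol/L reporting and about 31–70% at 0.1 mg/dL for n = 3 to 9, against about 1–10% on the ULN limb.

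The n/(n+1) result rests on exchangeable, untied values with no drug effect. The rounded figures also rest on the assumed mean, SD, ULN and CV. The mechanism needs only the *or* reading and that the footnote does not exempt the row.

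What is distorted is the Grade 1 creatinine count and the Grade 0-to-1 shift cell. Results for Grade 2 or higher, Grade 3 or higher, DLTs and CBR are essentially unaffected, and all analyses are descriptive. This is a cheap improvement to a safety table, not a threat to the trial's conclusions.

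**What to change.** Keep the CTCAE v4.03 grade. In the treatment-emergent summary and the shift table, split creatinine Grade 1 into:

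- (a) above ULN and up to 1.5 × ULN;
- (b) above baseline and up to 1.5 × baseline, but not above ULN.

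Report (a) plus Grade 2 or higher as the headline treatment-emergent creatinine incidence, and show (b) on its own line. State in Appendix 1 that the limbs are joined by *or*, and whether the footnote applies to this row. Record the split in SAP section 8.

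Deleting the baseline limb from Grade 1 would be a worse repair. It departs from the scale that the protocol specifies, and grades would jump from 0 to 2: with ULN 90, a move from 58 to 86 µmol/L (86/58 = 1.48) would be Grade 0, and a move from 58 to 88 (88/58 = 1.52) Grade 2.

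The cost is one extra table row, a few words in the SAP and a small programming change.

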11.2 Panel: Hematology

Lab Test	Unit	Grade 1	Grade 2	Grade 3	Grade 4
Hemoglobin increased	g/dL	Increase in >0 - 2 gm/dL above ULN or above baseline if baseline is above ULN	Increase in >2 - 4 gm/dL above ULN or above baseline if baseline is above ULN	Increase in >4 gm/dL above ULN or above baseline if baseline is above ULN	undefined
Hemoglobin decreased	g/L	[100, LLN)	[80, 100)	[0, 80); transfusion indicated	Life-threatening consequences; urgent intervention indicated
Platelet count decreased	10^9/L	[75, LLN)	[50, 75)	[25, 50)	[0, 25)
WBC increased	10^9/L	undefined	undefined	>100	undefined
WBC decreased	10^9/L	[3, LLN)	[2, 3)	[1, 2)	[0, 1)
Lymphocytes increased	10^9/L	undefined	(4, 20]	>20	undefined
Lymphocytes decreased	10^9/L	[0.8, LLN)	[0.5, 0.8)	[0.2, 0.5)	[0, 0.2)

Lab Test	Unit	Grade 1	Grade 2	Grade 3	Grade 4
Neutrophil count decreased	10 ⁹ /L	[1.5, LLN)	[1, 1.5)	[0.5, 1)	[0, 0.5)

11.3 Panel: Coagulation

Lab Test	Unit	Grade 1	Grade 2	Grade 3	Grade 4
International normalized ratio of prothrombin time (INR) increased	NA	(ULN, 1.5xULN]	(1.5xULN, 2xULN]	>2xULN	-
Activated partial thromboplastin time prolonged	Seconds	(ULN, 1.5xULN]	(1.5xULN, 2.5xULN]	>2.5 x ULN	-

11.4 Panel: Lipid Panel

Lab Test	Unit	Grade 1	Grade 2	Grade 3	Grade 4
Cholesterol high	mmol/L	(ULN, 7.75]	(7.75, 10.34]	(10.34, 12.92]	>12.92
Triglycerides high (hypertriglyceridemia)	mmol/L	(1.71, 3.42]	(3.42, 5.7]	(5.7, 11.4]	>11.4

* Conditions will not be checked programmatically.

Reference: https://www.eortc.be/services/doc/ctc/CTCAE_4.03_2010-06-14_QuickReference_5x7.pdf

12. APPENDIX 2 PROGRAMMING CODES FOR STATISTICAL ANALYSIS

Programming of the tables, listings and figures will be performed using SAS Version 9.4 or later, running under UNIX environment. The following table presents the SAS codes for the analyses of response endpoints.

Endpoint	Test	SAS Code
ORR, CBR	Clopper-Pearson (exact) 95% confidence interval	<pre>ods listing close; proc freq data = indata; ods output BinomialCLs=CI BinomialProp=prop; table objresp / binomial(level = 1 exact) out=freq1 (keep=objresp count); run; ods listing;</pre>
PFS, DOR, OS	Kaplan-Meier: median, 95% CI, 25th-75th percentile	<pre>ods listing close; ods output Quartiles=Quartile; proc lifetest data=indata; time timevar*censvar(1); run; ods output close; ods listing;</pre>

Signature Page for VV-CLIN-000247 v1.0

eSignature Approval Task	PPD
	Clinical 21-Feb-2023 16:30:29 GMT+0000

Signature Page for VV-CLIN-000247 v1.0

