6.5.2 Tumor and Response Evaluations

Tumor and response evaluations, PFS and DOR analyses will be based on the FAS and repeated on the Tumor Response Evaluable Set.

Tumor and response evaluations, PFS and duration of response analyses will be based on the FAS and Tumor Response Evaluable Subjects population. Data will be summarized by dose level in Dose Escalation and by cohort in Dose Expansion, and listed in by-subject listings in the Tumor Response Evaluable Subjects population.

Clinical Benefit Rate (CBR) is the primary endpoint for the Monotherapy Phase 2 and Combination Phase 2 and a secondary endpoint for the Monotherapy Escalation Phase 1, Monotherapy Expansion Phase 1, and Combination Escalation Phase 1. It is defined as the proportion of subjects who have at least one confirmed response of CR or PR (only if subject has measurable disease), or SD \geq 24 weeks (or non-CR/non-PD \geq 24 weeks for subjects with non-measurable disease) prior to any evidence of progression. Subjects who develop PD, intolerable toxicity or death or who discontinue study treatment prior to the first post-Baseline assessment will be classified as non-responders.

A confirmed response of CR/PR means that a response of CR/PR is recorded at one visit and confirmed by repeat imaging at least 4 weeks later with no evidence of progression between confirmation visits.

In case of SD, measurements should have met the SD criteria for a minimum interval of 8 weeks (8 weeks minus the 7-day visit window) following the start of treatment. Similarly, for non-measurable disease, non-CR/non-PD should be maintained for a minimum interval of 8 weeks (8 weeks minus the 7-day visit window) following the start of treatment.

Best overall response (BOR) will be derived for each subject, based on evaluation of response at each tumor assessment visit per investigator assessment using Response Evaluation Criteria in Solid Tumors (RECIST) version 1.1 and reported in the following categories:

- Complete Response (CR)
- Partial Response (PR)
- Stable Disease (SD)
 - SD \geq 24 weeks in duration
 - 8 weeks < SD < 24 weeks in duration
- Non-CR/non-PD
- Progressive Disease (PD)

- Non-Responders (NR)
- Not Evaluable (NE)

Confirmation of PR and CR responses will follow the confirmation process contained in the following table where the best two consecutive time points are considered.

Earlier Best Response (not yet confirmed)	Later Best Response (confirmation)	Best Overall Response
CR	CR	CR

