CR	No CR or missing	SD
PR	CR or PR	PR
PR	SD or PD or missing	SD
SD	NA – no confirmation needed	SD
PD	NA	PD

Responses recorded after initiation of anti-tumor therapy are not used (not evaluable) nor are PD responses after a missed visit [>126 days has elapsed since the last image-based response assessment (or first dose date if no prior response)] up to 24 weeks after C1D1. If the previous evaluable image-based response assessment is more than 24 weeks after C1D1, a PD response is considered to be "missed" if more than 26 weeks (182 days) has elapsed. In the case of stable disease, measurements should have met the stable disease criteria for a minimum interval of 8 weeks (8 weeks minus the 7-day visit window = 49 days) following the start of treatment.

Duration of SD for subjects with best overall response = SD is defined as the time from the day of first study treatment to the start of radiologic disease progression or death. If the subject does not have a radiological disease progression or death, the duration of SD is defined as the time from the day of first study treatment to the date of the last SD assessment. Taking scheduling of imaging into account, a 1 week window will be utilized such that the threshold for 24 weeks will be $23*7 = 161$ [response date – first dose date +1 ≥ 161].

When the investigator is in doubt as to whether progression of disease has occurred and therefore reassesses the subject at a later date, the date of the initial scan should be declared as the date of progression if the repeat scans confirm progression.

Objective Response Rate (ORR) is a secondary endpoint for all cohorts. It is defined as the percentage of subjects with measurable disease who have at least one confirmed response of CR or PR prior to any evidence of progression (as defined by RECIST v1.1). Subjects who develop PD, intolerable toxicity or death or who discontinue study treatment prior to the first post-Baseline assessment will be classified as non-responders.

Data obtained up until progression, or last evaluable assessment in the absence of progression, will be included in the assessment of ORR. However, any complete response or partial response which occurred after a further anticancer therapy was received will not be included in numerator of the ORR calculation.

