The change from Baseline and percent change from Baseline will be calculated for each response assessment for the sum of target lesion measurements. The best (minimum) percent change from Baseline will be identified for each subject.

For further details regarding response criteria, refer to protocol Appendix 2 – Tumor Response Criteria.

Best overall response will be summarized categorically based on the four RECIST categories: complete response (CR), partial response (PR), stable disease (SD) and progressive disease (PD). The summary will also include a category for unevaluable (NE) subjects if applicable and one for non-responders (NR). PR and CR must be confirmed by repeat imaging at least 4 weeks later with no evidence of progression between confirmation visits.

The clinical benefit rate (CBR) and objective response rate (ORR) estimates will be presented along with the associated Clopper-Pearson 95% CIs.

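### The Appendix 2 code for CBR and ORR picks the response level by table position with no stated coding, so any cohort without a responder prints as 100%, and under 0/1 or N/Y coding the rate is inverted

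*SAP*

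**What the plan says.** SAP 6.5.2 is clear about what is to be reported. For CBR, "It is defined as the proportion of subjects who have at least one confirmed response of CR or PR", with stable disease of at least 24 weeks also counting. CBR "is the primary endpoint for the Monotherapy Phase 2 and Combination Phase 2", and it is secondary in the Phase 1 parts. "Objective Response Rate (ORR) is a secondary endpoint for all cohorts", restricted to subjects with measurable disease. For both rates the "estimates will be presented along with the associated Clopper-Pearson 95% CIs". SAP 6.1 adds that "95% CIs for binary variables will be calculated using the binomial distribution (exact method) and will be 2-sided", unless stated otherwise.

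Appendix 2 of the SAP has a single code entry for ORR and CBR, labelled "Clopper-Pearson (exact) 95% confidence interval". Its operative line is "table objresp / binomial(level = 1 exact) out=freq1". The block has no `order=` option, no format, no quoted level value and no step that fills in an absent level. Neither the SAP nor the protocol says how `objresp` is coded.

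**The concern.** The text asks for the proportion with benefit or response. The code asks for the proportion in whichever level stands at position 1 of the table. The two agree only if responders sort ahead of non-responders and at least one responder is present, or if every subject in the cohort is a responder.

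Two failures follow. One needs no assumption about coding: with no responder, the only level in the table is non-response, and its share is 100%. The other depends on coding: with 0/1 or N/Y, non-response sorts ahead of response, and the program reports the complement of the rate and of its interval.

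At stake are the primary estimate of the two Phase 2 parts (CBR) and a secondary estimate in every cohort (ORR). This is the only code the SAP gives for either. If the validation programmer also follows Appendix 2, double programming would agree on the wrong number.

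**Working it through.** **Inputs.** Up to 75 subjects per dose level in Monotherapy Phase 2, with a hypothesised CBR of 40-50% and precision of ±12 points (protocol 9.2.3). 19 + 32 = 51 evaluable subjects per dose cohort in Combination Phase 2, 50% against 70%, with Stage 1 futility at 10 or fewer of 19 (protocol 9.2.4, SAP 3.4). 3 to 6 evaluable subjects per escalation dose cohort (SAP 3.1). Subgroups shown from n = 5 (SAP 6.5.2.1). The coding of `objresp` is not given, so three codings are tried: 0/1, N/Y, and 1 = responder with 2 = non-responder. The reading of `level=` is standard PROC FREQ behaviour, not something the documents state. The line was emulated (sort the levels present, take the first, compute its exact interval), not run in SAS.

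**1. The plan's own figures.** Clopper-Pearson for 30/75 is 28.9-52.0%, so the half-widths are 40.0 − 28.9 = 11.1 and 52.0 − 40.0 = 12.0 points. For 38/75 = 50.7% the interval is 38.9-62.4%, about 11.8 points each way. The stated ±12 reproduces. For the Simon design, P(10 or fewer of 19 | CBR 50%) = 67.6%, against 68% stated. Taking success as more than 32 of 51, a cut-off the documents do not print, alpha is 0.0219 and power 80.1%. The design reproduces, so the problem lies in the code alone.

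**2. No responder, any coding.** The correct interval for 0/n runs from 0 to 1 − 0.025^(1/n). The printed line treats the cohort as n/n, which runs from 0.025^(1/n) to 1.

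| Cohort | Correct | Printed line, all three codings |
|---|---|---|
| 0/3 | 0% (0-70.8%) | 100% (29.2-100%) |
| 0/5 | 0% (0-52.2%) | 100% (47.8-100%) |
| 0/6 | 0% (0-45.9%) | 100% (54.1-100%) |
| 0/10 | 0% (0-30.8%) | 100% (69.2-100%) |

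**3. At least one responder and one non-responder.** Here the result depends on the coding.

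| Cohort | Correct; also the printed line if 1 = responder, 2 = non-responder | Printed line if 0/1 or N/Y |
|---|---|---|
| 30/75 | 40.0% (28.9-52.0%) | 60.0% (48.0-71.1%) |
| 38/75 | 50.7% (38.9-62.4%) | 49.3% (37.6-61.1%) |
| 36/51 | 70.6% (56.2-82.5%) | 29.4% (17.5-43.8%) |

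When all n subjects respond, the line is right under every coding. So under 0/1 or N/Y both 0/n and n/n print as 100%.

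**4. How often a cohort has no responder.** P(0 of m) = (1 − p)^m. The documents give no expected ORR, so 5%, 10% and 20% are assumptions; 40% is the lower end of the protocol's hypothesised CBR.

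| True rate | m = 3 | m = 6 |
|---|---|---|
| 5% | 86% | 74% |
| 10% | 73% | 53% |
| 20% | 51% | 26% |
| 40% | 22% | 5% |

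At m = 75 and 40% the chance is negligible. The failure that needs no coding assumption is therefore mainly a matter of ORR in small escalation cohorts and subgroups.

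**The case against.** The best defence is that the governing text is right. SAP 6.5.2 defines both rates as proportions with benefit or response and names the interval, and a programmer who tabulated non-responders would contradict it. The code also looks like a template: it has generic dataset and variable names, one variable for two endpoints, and no split by study part or dose level, so it must be adapted before it can produce any planned table. SAP 1 describes the plan as flexible guidance, and SAP 4 refers to a separate programming QC plan. The code saves the counts by level, and best overall response is tabulated separately, so an ORR of 100% beside no CR or PR should be noticed.

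Much of this stands, and it lowers the severity. It does not make the line right. Appendix 2 does not label the code as an example, and neither the flexibility wording nor the reference to a QC plan supplies the coding or a zero-responder rule. Visibility is also weakest where Monotherapy Phase 2 expects to be: at 38/75 the inverted result, 49.3%, looks as plausible as the true 50.7%.

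A reader might go further and infer that the primary CBR will be reported inverted. The documents do not support that, because the coding is not given and a coding with responders sorted ahead gives the right answer whenever someone responds. Nor does "time timevar*censvar(1" in the survival code settle it: that 1 marks the censoring value of a different variable.

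**Conclusion.** The printed line is wrong as written, not merely short on detail, because it gives 100% in place of 0% in any cohort or subgroup without a responder under every coding. The inversion of the rate in other cohorts is conditional on 0/1 or N/Y coding. Both statements rest on the standard PROC FREQ reading of an unquoted level number, which a single test run on a 0/n cohort would settle.

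The certain failure falls mainly on small Phase 1 dose cohorts and subgroups, where in the Phase 1 parts both endpoints are secondary and the error would usually be seen. The conditional failure could reach the Phase 2 primary CBR, where 40% would print as 60%. It would be a mistake to extend the point to the design: the definitions, the Clopper-Pearson method and the sample sizes hold, and the Simon futility rule is a count that does not use this code. Severity: a moderate correction, not one on which the plan stands or falls.

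**What to change.** In SAP Appendix 2:

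- State the coding of `objresp`, and that it is derived separately for CBR and ORR.
- Select the responder by its quoted formatted value, for example `level='1'` or `level='Y'`, as the coding requires.
- A quoted value alone does not create an absent category. Supply a count dataset holding both levels for each cohort and use `weight count / zeros`, or state a rule that a cohort with no responder is reported as 0 of n with its exact interval.
- Test the program on a 0/n cohort and an n/n cohort.
- Check whether any table already produced used the printed line. The SAP is dated 17 February 2023 and cites a data cut-off of 18 May 2022 (SAP 8), so output may exist.

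The cost is a few lines of code, a small count dataset per cohort and two test runs. No definition, sample size or decision rule changes.
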